Project Information:

Project Code : A21010491

Title : Promotion of Breast Milk Donation in Breastfeeding Mothers Through a Mobile Health Intervention Utilizing an Innovative Technological Tool

Research Line : Nutrition and Human Development

Location : Metropolitan Lima Area

Ethical evaluation record of research studies: Study code N°: 0123-2023

Approval Date : July 21, 2023

I. Executive Summary:

In Peru, 71% of preterm newborns (PN) die due to various complications during their recovery. Breastfeeding in preterm infants is often interrupted, necessitating donated breast milk (BM). Human Milk Banks (HMB) serve as critical allies in reducing mortality rates among preterm newborns; however, the number of donors is insufficient to meet current demand. Low donation rates are attributed to a lack of awareness regarding BM donation, as well as perceptions, beliefs, and attitudes that influence the predisposition to donate. As a solution, the development of an Innovative Technological Tool (ITT), the Amamantapp mobile application, has been developed to promote a culture of BM donation. For the development of the intervention, the Design Thinking methodology was employed to identify participant requirements, prioritize key topics, and define the most suitable ITT. A randomized controlled trial (RCT) will be conducted involving breastfeeding mothers treated at the National Maternal and Perinatal Hospital (NMPH). Subsequently, the mobile application will be implemented over a 60-day period within the intervention group. Knowledge, attitudes, and practices will be evaluated using a KAP questionnaire before and after the intervention.

II. Keywords:

Human Milk Bank, Breast Milk Donation, Breastfeeding

III. Background:

International Background

A study published in 2016 implemented an intervention using a bilingual and interactive educational program on tablets regarding breastfeeding; this achieved increased knowledge of the subject and breastfeeding intention (1). In 2017, another study developed an intervention program through a website that consisted of exchanging advice, resolving doubts, and providing follow-up to participating breastfeeding mothers. The study concluded that the program had a positive effect on breastfeeding duration rates during the 6-month follow-up period (2). In 2018, a study conducted in Thailand consisted of an intervention to promote breastfeeding through a mobile application. It was concluded that the application has high utility for mothers, but usability was low due to design aspects (3).

In 2020, an observational study based on the description of a breastfeeding mobile application found that the support provided by the tool is linked to the needs corresponding to the infant's developmental stage. Between 15 days and 3 months of age, mothers consult on topics such as breastfeeding crises/complications and returning to work. From 3 months to 1 year, mothers seek support on issues related to complementary feeding and weaning. When the user's infant reaches 1 year of age, the most searched topics are weaning and breastfeeding (4)

National Background

A study conducted in Lima, Peru, in 2019 regarding beliefs, attitudes, and practices (BAP) surrounding breast milk (BM) donation found that 98.2% of those surveyed believe that BM is the best food for both healthy and ill newborns. Additionally, while 75.7% had heard of Human Milk Banks (HMB), they were unaware of their locations. Furthermore, although the majority of participants agreed with donating to an HMB, only 16.5% had ever donated (5).

State of the Art

BM provides the ideal balance of nutrients for the infant, containing bioactive ingredients such as immunoglobulins, hormones, oligosaccharides, and others (6,7). Children who do not receive BM are at a higher risk of suffering from gastrointestinal, respiratory, and urinary infections, which may be more severe and lead to hospital admissions; in the long term, they face an increased risk of asthma, obesity, diabetes mellitus, and cancer (8).

In preterm newborns, BM decreases the prevalence of necrotizing enterocolitis, digestive intolerance to enteral feeding, bronchopulmonary dysplasia, nosocomial infections, retinopathy of prematurity, neurocognitive delay, and re-hospitalization after discharge (9). When circumstances do not allow for breastfeeding, the HMB becomes vital. This bank is responsible for the promotion and support of breastfeeding, as well as the collection, processing, quality control, and dispensing of donated BM to any child in need, particularly the preterm newborn (10).

To fulfill its mission, the HMB requires donors; therefore, it is vital to provide them with sufficient information and support regarding breastfeeding and BM donation, as the possibilities of successful breastfeeding increase the likelihood of them becoming donors (9). The appropriation of BM donation practices depends largely on the dissemination of positive experiences regarding breastfeeding and donation, internalized scientific knowledge, and the positioning of the topic in the media (11).

In recent years, the use of mHealth interventions to promote breastfeeding has expanded due to the widespread use of mobile phones. In Peru, 82% of citizens access the internet via a mobile phone. mHealth is defined as digital technological tools and resources used to capture, manage, store, and exchange information through mobile devices (12,13). Evidence suggests that mHealth has the potential to promote, educate, and support breastfeeding women. It is noteworthy that there is limited evidence regarding mHealth interventions aimed at fostering BM donation (4,14).

Problem Statement

PAHO and WHO (2019) demonstrated that, globally, 45% of children under 2 years of age were breastfed (15, 16). In Peru, 66.4% of infants consumed BM, with this percentage being higher in the Andean region (77%) and rural areas (79.6%) (17).

Even though breastfeeding is widely practiced in Peru, there are cases where breastfeeding is interrupted: low-birth-weight newborns (LBW) with a risk of digestive pathology or immune deficiency, and newborns whose mothers cannot provide sufficient milk due to various health reasons. These infants are candidates to receive donated BM (18).

At a global level, evidence shows that during the 2009–2015 period, there were 1,563,240 female donors, with South America being the region with the highest percentage of donors (96.6%) (19). In Peru, the first HMB was founded in 2010 at the NMPH. The number of donors increased from 368 to 1,642 in the 2010–2018 period (10). However, this increase is insufficient to cover the growing annual rate of preterm births (1,620), which demand approximately 500 liters of donated BM per month (20). This situation has worsened in the context of the COVID-19 pandemic, which reduced the number of monthly donors from 200 to 50 (20).

Evidence shows that factors related to the low number of BM donors include perceptions, beliefs, and attitudes such as: the belief that donating carries a risk of transmitting HIV or cancer, and a low interest in donating due to lack of knowledge (21).

As part of the profile development for this project, interviews were conducted with breastfeeding mothers and healthcare personnel to understand their perception of BM donation. The results revealed a lack of knowledge regarding HMBs and BM donation, and a perception among mothers that they should exclusively donate when they have surplus milk. However, upon learning about the assistance they could provide to newborns, they adopted a positive attitude toward donation (22).

Based on the above, there is clear evidence of a real problem concerning the deficit of human milk donors in Peru.

IV. Justification:

Considering that the proportion of deaths among preterm newborns in the country has increased over the last decade (from 62.6% in 2011 to 71% in 2019) (23), it is necessary to promote knowledge regarding BM donation to favor an increase in the volume of such donations.

The WHO states that BM promotes the cognitive and sensory development of infants, in addition to protecting them against various diseases and aiding in their prompt recovery (24). Low-birth-weight preterm newborns face a high risk of growth failure and comorbidities that result in neurodevelopmental delay and lower academic performance; likewise, it has been demonstrated that BM intake is beneficial in reducing hospital stay and complications, and is associated with a larger head circumference and better scores in global and verbal cognitive areas at five years of age (25). Since the first HMB was inaugurated in Peru in 2010, the quantity of BM donations has been increasing; thus, by 2018, the NMPH in Lima managed to collect 1,390 liters of BM between January and October, benefiting 1,771 preterm infants (26). However, the demand for donations exceeds the amounts donated, meaning that not all infants who may require this nourishment are able to obtain it. Additionally, in 2020, the newspaper La República reported on the reduction of BM donations due to the quarantine context facing Peru at that time (20).

In summary, there is a need to implement a project that fosters knowledge of BM donation to benefit preterm infants, their families, and the country across different dimensions. Furthermore, this study is designed as a randomized controlled trial, which will allow us to accurately measure the effect of our mobile intervention on breastfeeding mothers, aiming to provide a robust and reliable scientific contribution to solve this problem and save the lives of more preterm infants.

V. Contribution and Impact:

The project will allow for the assessment of the success of mHealth implementation through the use of an ITT, Amamantapp mobile application, which may serve as a precedent for the future implementation of educational projects under this modality. This will assist in the dissemination of this and other health-related topics of interest in various regions of the country. Furthermore, the results of this trial will offer a deeper understanding of mothers' diverse perspectives regarding the promotion of BM donation and the potential for these

types of interventions to increase knowledge levels concerning BM donation and the status of HMBs.

Simultaneously, this work seeks to contribute to and foster the development of future research related to the proposed topic, as it is unfortunately not yet widely disseminated, and similar projects to the one proposed are currently lacking.

Finally, the use of this project as a baseline for a multicenter study is suggested, involving all HMBs in Peru to provide more robust and significant evidence. This would allow for an adequate approach to the target population, leading to an increase in the number of BM donors with the goal of decreasing the neonatal mortality rate and, consequently, generating a positive impact on the country's public health.

VI. Hipótesis:

General Hypothesis:

- The intervention through an Innovative Technological Tool promotes breast milk donation among breastfeeding mothers.

Specific Hypotheses

- The intervention through an innovative technological tool increases the knowledge level regarding breast milk donation among breastfeeding mothers.
- The intervention through an innovative technological tool improves the attitude toward breast milk donation among breastfeeding mothers.
- The intervention through an innovative technological tool increases the proportion of breastfeeding mothers who initiate breast milk donation practices.

VII. Objectives:

General Objective:

To evaluate the effect of an intervention using an innovative technological tool on the promotion of breast milk donation among breastfeeding mothers.

Specific Objectives:

- To measure the effect of an intervention using an innovative technological tool on the level of knowledge regarding breast milk donation among breastfeeding mothers.
- To evaluate the effect of an intervention using an innovative technological tool on the attitude toward breast milk donation among breastfeeding mothers.
- To identify the effect of an intervention using an innovative technological tool on the proportion of breastfeeding mothers who initiated breast milk donation practices.

VIII. Methodology:

Research Design

A randomized controlled trial (RCT) will be conducted.

Population and Sample

Sampling for the Qualitative Component

- **Population:** Breastfeeding mothers treated at the National Maternal and Perinatal Hospital (NMPH).
- **Sample Size:** 10 breastfeeding mothers (in-depth interviews), determined by non-probability sampling.

Inclusion Criteria:

- Breastfeeding mothers within 40 days postpartum.
- Breastfeeding mothers with living children.
- Breastfeeding mothers who have access to an Internet connection.
- Breastfeeding mothers who have the necessary equipment to access platforms with video-calling capabilities.
- Breastfeeding mothers who are proficient in the use of platforms with video-calling capabilities.

Exclusion Criteria:

- Mothers for whom breastfeeding is contraindicated.
- Breastfeeding mothers with a diagnosis of mental illness.
- Breastfeeding mothers who are or have been donors to the Human Milk Bank of the National Maternal and Perinatal Hospital.

Sampling for Intervention Development

Population: Breastfeeding mothers treated at the National Maternal and Perinatal Hospital (NMPH).

Sample Size: The sample size was determined using the OpenEpi program, with the option “Sample size to compare two means”, considering a IC of 95%, a power of 80%, a sample size ratio equal to 1, a minimum mean difference of 2.1 (in the breastfeeding knowledge score) and a SD of 3.4 for both groups, similar to that found in the study by Joshi et al (1).

Therefore, the net sample size required for this study was 86 participants, distributed as follows: 43 in the control group and 43 in the intervention group. However, considering a potential loss of 30% between the initial and the final assessment, the sample size was increased by 112 mothers in total.

Inclusion Criteria:

- Breastfeeding mothers within 40 days postpartum.
- Breastfeeding mothers with living children.
- Breastfeeding mothers with an active Internet connection.
- Breastfeeding mothers who possess the technological equipment required to access the innovative technological tool (smartphone, tablet, or computer).
- Breastfeeding mothers residing within the jurisdiction of the National Maternal and Perinatal Hospital.

Exclusion Criteria:

- Breastfeeding mothers who are illiterate.
- Breastfeeding mothers with a diagnosis of mental illness.
- Breastfeeding mothers with significant difficulties in operating technological equipment.
- Breastfeeding mothers who are current users of any milk bank.
- Breastfeeding mothers who are or have been donors to the Human Milk Bank of the National Maternal and Perinatal Hospital.

Techniques and procedures

The time of participation in the study will be approximately 3 months, divided into the following phases: enrollment (15 days), baseline assessment (7 days), exposure to the intervention (60 days), and final assessment (7 days).

The development of the mobile intervention was based on the Human-Centered Design (HCD) approach (27). *AmamantApp* app includes modules on breastfeeding basics, benefits of breastfeeding for mother and child, breast milk donation, benefits of donating breast milk, myths and beliefs about human milk donation, requirements to be a donor, and where to donate.

To reduce bias, participants will be randomly assigned to the intervention and control groups in a 1:1 ratio according to their order of inclusion in the study. A master randomization list will be generated using the Spanish version of the free OxMaR software (28).

The intervention group will receive education on human milk donation via a mobile app, and the control group will receive information on human milk donation through printed leaflets. The app will be installed and explained to the mothers with hospital discharge orders on their mobile phones. The intervention will continue while the mothers are at home. The research team will hold an interactive session to introduce the mobile app to the participants. This will begin with an initial explanation of the app's features, followed by a period in which participants will be able to explore and use the application in real time. Furthermore, participants will receive weekly training on how to use the app to reinforce their knowledge of its operation.

The intervention period will last 60 days, during which knowledge, attitudes, and practices (KAP) will be assessed using a KAP questionnaire. This instrument will be administered face-to-face at baseline (pretest) and online via Google Forms after the intervention (posttest).

Design and Evaluation of the Mobile App

The process of designing the intervention with the Amamantapp app was based on Human Centered Design (HCD) through the application of the Design Thinking technique [29, 30]. This technique consisted of 6 stages:

Stage 1: Recognition

Aimed at empathizing, researchers defined the user profile, as well as the sociodemographic characteristics of the breastfeeding mothers. In this stage, 12 in-depth interviews were used to collect information concerning their KAP related to breastfeeding/breastmilk donation and the use of technology. At this stage, it was found that mothers were not aware that they

could donate their breast milk, nor were they aware of the existence of HMB. The mothers also expressed a favorable attitude towards human milk donation, but stated that they had not engaged in that practice due to a lack of knowledge.

Stage 2: Identification of Needs

An empathy map was drawn up with the responses obtained to identify the needs of the users and the prioritization of the issues to be addressed regarding breastfeeding and milk donation. In this second stage, the mothers' need for easily accessible information on human milk donation, the requirements to be a donor, the mechanisms for donating, and the locations of human milk banks were identified.

Stage 3: Ideation of Solutions

A team of 6 researchers devised different innovative solutions (eg, digital educational booklet, mobile app, telephone counselling, SMS, and MMS), which were then evaluated using the impact and innovation matrix; a vote was taken considering the criteria of impact, innovation, added value, and scalability. Finally, the mobile app was the top-rated vote.

Stage 4: Prototyping

The intervention is prototyped as a mobile app, based on the HCD model [27,31]. This model comprises sequential phases that range from defining the user requirement, designing the proposal, and through the implementation, verification, and maintenance of the intervention with the mobile app. The prototype was developed following the sequence previously described, which involved outlining the didactic content, the bibliographic search for educational content, the search for graphic resources, and the design of the screens, sections, and navigation routes.

The design process followed an iterative User Centered Design approach [32], incorporating feedback from experts in nutrition, health technology, human-computer interaction, and software development. The app employed a wireframe-based development approach, allowing early feedback on design decisions before implementation. The frontend was built with Flutter's Dart programming language, a cross-platform mobile development framework, to ensure broad accessibility on Android and iOS devices. The backend relies on a cloud-based infrastructure for data processing and secure storage. The app features personalized content delivery, ensuring that users receive relevant donation guidelines based on their location and eligibility. In addition, it includes built-in accessibility features, such as adjustable text sizes, to accommodate the diverse needs of users. The technical architecture prioritizes scalability, allowing for potential expansion across Peru and multiple countries in Latin America.

Stage 5: Usability Evaluation

The content was validated through an iterative process to improve the technological innovation tool until its final version. This iterative process evaluated the usability of the mobile app through a mixed study with a quantitative and qualitative phase that determined the experience of 32 breastfeeding mothers hospitalized in the postpartum ward of a mother and child hospital in Lima. As a result, the application of a validated 5-point Likert scale reported usefulness and satisfaction of the tool and ease of use with scores of 4.1. Access to information and comfort of use scored 4.3 and 3.9, respectively. These positive ratings demonstrated the high usability of the app. The results of the in-depth interviews during the validation of Amamantapp showed that users highlighted the detailed information on milk

donation, the ease of donating, and recommended the use of the mobile app because it provides mothers with relevant information.

Stage 6: Effect Evaluation

With the final version of the technological innovation tool, the randomized controlled trial will be implemented for a period of 60 days. The research team will continuously conduct field evaluations of the tool's performance (verification) and ensure the maintenance of the intervention through push notifications, reminders, text messages (SMS), or other complementary resources. At this stage, a baseline and final measurement of indicators will also be assessed for both the intervention and control groups using a KAP questionnaire developed by the researchers. As part of this last stage, the qualitative component of the evaluation of the effect of the mobile intervention will be implemented. Purposive sampling will be used to recruit participants. Any breastfeeding mother from the intervention group who has completed the mobile intervention will be eligible to take part.

Analysis Plan

Qualitative Analysis Plan

The information gathered from the in-depth interviews will be transcribed, processed, and analyzed using specialized qualitative data analysis software. Consequently, matrices and graphic organizers will be generated.

Statistical Analysis Plan

The information collected during the intervention will be processed in MS Excel and analyzed using IBM SPSS statistical software.

Inferential analysis will be by intention to treat (ITT), to ensure the equivalence of the study groups. The sociodemographic and baseline characteristics of the control and intervention groups will be compared using Pearson's Chi-square test, Fisher's exact test, or Student's t-test, depending on the type of variable.

To determine the effect of the intervention, changes in milk donation knowledge scores among breastfeeding mothers in the intervention group will be compared with the control group throughout the study period (baseline and endline variation) using a double difference regression model.

For qualitative variables (attitudes, practices), a Cochran's Q test will be applied to evaluate changes following the intervention period. Regarding donation practices, Fisher's exact test will be applied, and the Odds Ratio (OR) will be calculated to determine the utility of the intervention in breast milk donation. Finally, only descriptive statistics will be presented regarding user satisfaction.

Ethical Considerations

All procedures will be conducted in accordance with the Declaration of Helsinki. After identifying that the applicants meet the inclusion criteria, they must sign an informed consent form to formalize their enrollment in the intervention. In this study, participants' personal information will be collected and stored. This information will only be used to monitor the proper execution of the intervention (exposed group) and for coordination purposes (unexposed group). Participants will be identified using codes (anonymization), and their

personal information will be stored in a separate file, which will be deleted once the intervention concludes. In addition, the data collected were coded to ensure privacy and confidentiality.

IX. Referencias bibliográficas:

2. Darias AG. Evaluation of the "sponsor a first-time mother" intervention program in the promotion of breastfeeding [Internet]. [San Cristóbal de La Laguna]: University of La Laguna; 2017 [cited 2021 Feb 27]. Available from: <https://dialnet.unirioja.es/servlet/tesis?codigo=236035>

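### The 30% loss allowance multiplies 86 by 1.3 instead of dividing by 0.7, so at 30% loss 112 mothers leave about 39 per arm, not 43, and power is below the stated 80%

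*Combined protocol and SAP*

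**What the plan says.** The calculation is in the combined protocol and SAP, Methodology, Sampling for Intervention Development, under Sample Size. It compares two means in OpenEpi with these inputs:

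- confidence level, power and allocation: "considering a IC of 95%, a power of 80%, a sample size ratio equal to 1"
- effect: "a minimum mean difference of 2.1 (in the breastfeeding knowledge score")
- variability: "a SD of 3.4 for both groups"

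The result is given as "the net sample size required for this study was 86 participants, distributed as follows: 43 in the control group and 43 in the intervention group". The next sentence makes the allowance for attrition: "considering a potential loss of 30% between the initial and the final assessment, the sample size was increased by 112 mothers in total".

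The Statistical Analysis Plan section names intention to treat and a difference-in-differences regression for the knowledge score. It gives no method for mothers who have no final score. No other section revises the enrolment figure.

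**The concern.** The plan defines the loss as mothers assessed at the start but not at the end. The 30% is therefore a fraction of those enrolled, and the enrolled number N must satisfy N × 0.70 ≥ 86. Adding 30% to the net figure solves a different equation and always gives too few.

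Knowledge is the only outcome with a sample-size calculation. If the allowance is wrong, the trial does not have the stated power under the loss it says it is prepared for. Anyone who checks the arithmetic will find this quickly.

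**Working it through.** **Inputs, all from the Sample Size paragraph.** Difference 2.1; SD 3.4 in both arms; power 80%; ratio 1:1; net size 86 (43 per arm); loss 30%; total 112. Alpha is 0.05, from the 95% confidence level. Two-sided testing is assumed because sidedness is not stated; a one-sided calculation gives 33 per arm and does not match the plan.

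**1. Reproduce the net size.**

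n per arm = 2 × SD² × (z₀.₉₇₅ + z₀.₈₀)² / difference² = 2 × 3.4² × (1.960 + 0.842)² / 2.1² = 41.15, so 42.

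With the t distribution, power is 79.9% at 42 per arm and 80.8% at 43, so 43 is the t-based answer. The plan's 86 is sound for these inputs.

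**2. Reproduce the total.**

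- 86 × 1.3 = 111.8, which rounds to 112, the stated figure.
- 86 / 0.7 = 122.9, so 123, which is not the stated figure.

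**3. What 112 leaves after 30% loss.**

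112 × 0.70 = 78.4 in total, or 39.2 per arm. The shortfall is about 4 per arm.

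**4. Power at the retained size.**

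Normal approximation: power = Φ(2.1 / (3.4 × √(2/n)) − 1.960).

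- n = 43: Φ(2.864 − 1.960) = 81.7%
- n = 39: Φ(2.727 − 1.960) = 77.9%

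Detectable difference, normal approximation: 3.4 × 2.802 × √(2/n), which is 2.05 at n = 43 and 2.16 at n = 39. The t-test figures use the noncentral t distribution with 2n − 2 degrees of freedom.

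| Per arm | Power, t-test | Power, normal | Detectable at 80%, t-test | Detectable at 80%, normal |
|---|---|---|---|---|
| 43 (required) | 80.8% | 81.7% | 2.08 | 2.05 |
| 39 (112 less 30%) | 76.8% | 77.9% | 2.18 | 2.16 |

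Both methods put power below 80% and the detectable difference above 2.1.

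**5. Loss that 112 can absorb.**

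1 − 86/112 = 23.2%.

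**6. Enrolment that would meet the plan's claim.**

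43 / 0.70 = 61.4, so 62 per arm and 124 in total. Check: 62 × 0.70 = 43.4 per arm, which meets 43.

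**7. The literal reading.**

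An increase by 112 gives 86 + 112 = 198, of whom 198 × 0.70 = 138.6 remain. There would be no shortfall. But 112 matches 86 × 1.3 and the sentence describes it as a total, so 112 enrolled is the only sensible reading.

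**The case against.** The best case on the other side accepts the arithmetic and disputes its weight.

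- **The loss is only potential.** With no loss, 56 per arm give about 90% power. At 20% loss, 112 × 0.80 / 2 = 44.8 per arm remain and power is above 80%. This is true, so the finding must be stated as conditional on 30% loss. But 30% is the plan's own figure, and the allowance exists to protect power at that figure.
- **The gap is small and depends partly on the formula.** Against the stated 80%, the shortfall is 2 to 3 percentage points. On the normal approximation 42 per arm would suffice, and 112 would then tolerate 1 − 84/112 = 25% loss. This also stands, but 30% exceeds either limit.
- **The planned model is not a simple comparison of two means.** This stands as a limit on what any restated power means. Suppose 2.1 is the difference in change and 3.4 the SD at each time point (both assumptions). The SD of change is then 3.4 × √(2(1 − ρ)). At 39 per arm, t-based power is about 62% for a baseline–endline correlation ρ of 0.3, 77% for 0.5 and 94% for 0.7. The documents give no correlation, so this cannot rescue the stated 80%; it could equally lower it.
- **The inputs are borrowed.** The sizing uses a breastfeeding knowledge score from a cited study, while the analysis concerns knowledge of milk donation. Uncertainty in 2.1 and 3.4 may matter more than four mothers per arm. That is a separate weakness and does not make the loss allowance correct.
- **Intention to treat keeps everyone in.** The plan gives no way of handling missing final scores, and a mother without one has no observed change. The plan itself calls 86 a net requirement.

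**Conclusion.** The concern holds. The loss allowance is miscalculated, and 112 mothers do not give 80% power if 30% are lost. About 39 per arm remain, with 76.8% power (t-test) or 77.9% (normal approximation), about 4 points below what 43 per arm would give.

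This rests on two-sided alpha of 0.05, the full 30% loss falling about equally on the arms, no information from mothers without a final score, and the two-mean comparison used in the plan. The error does not threaten the validity of the trial. It makes a design statement false as written, and that statement must be corrected.

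**What to change.** Replace the attrition sentence. Suggested text:

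> A total of 112 mothers will be enrolled (56 per arm). If 30% are lost before the final assessment, about 39 per arm will remain, giving about 77% power in a two-sided two-sample comparison of means for a difference of 2.1 points (SD 3.4). The required 43 per arm are retained for losses of up to 23%.

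This needs no extra mothers and changes no procedure. The cost is one sentence and a slightly less favourable stated power. Naming the two-mean comparison avoids implying that 77% applies to the regression model, and the new wording removes the ambiguity between 112 and 198.

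If the sponsor prefers to keep 80% power with 30% loss, the total must read 124 (62 per arm), which is 124 − 112 = 12 more mothers. Restating the power is sufficient.

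### The device criterion accepts a computer, but the app is described only for Android and iOS and is installed on mobile phones

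*Combined protocol and SAP*

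**What the plan says.** Under Sampling for Intervention Development, Inclusion Criteria, a mother must have an active internet connection and possess the "technological equipment required to access the innovative technological tool (smartphone, tablet, or computer". The three devices are listed as alternatives. The nearest exclusion criterion is "Breastfeeding mothers with significant difficulties in operating technological equipment", which concerns skill and not the type of device.

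Techniques and procedures describes delivery: "The app will be installed and explained to the mothers with hospital discharge orders on their mobile phones". The control group receives printed leaflets, which need no device.

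Stage 4 (Prototyping) says that the app was built with "a cross-platform mobile development framework, to ensure broad accessibility on Android and iOS devices". No web or desktop version is described anywhere. Stage 6 (Effect Evaluation) adds that the intervention is kept up through push notifications, reminders, text messages or other resources.

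The Statistical Analysis Plan states: "Inferential analysis will be by intention to treat (ITT), to ensure the equivalence of the study groups". No section says what happens if a mother allocated to the app has no device that can run it.

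**The concern.** The eligibility text and the delivery text describe different sets of mothers. Someone who screens from the criterion as written could enrol a mother with a computer and no smartphone or tablet. If she were allocated to leaflets, nothing would go wrong. If she were allocated to the app, she could not be exposed to it as the plan describes it.

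Under intention to treat she is analysed in the app arm. Each such mother contributes roughly a control-like outcome to that arm, so the estimated difference shrinks towards zero and power falls. The sample size leaves little slack, because 43 per arm sits just above the 80% target.

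Tablets raise a smaller inconsistency. They are eligible, and an Android or iOS tablet fits the platform description, but the installation text mentions only mobile phones.

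**Working it through.** **Texts side by side**

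| Device owned | Eligible as written? | Covered by the platform text (Stage 4)? | Covered by the installation text (Techniques and procedures)? |
|---|---|---|---|
| Android or iOS smartphone | Yes | Yes | Yes |
| Android or iOS tablet only | Yes | Yes | Not mentioned |
| Computer only | Yes | No | No |

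**Inputs.** All come from the sample-size paragraph: "considering a IC of 95%, a power of 80%, a sample size ratio equal to 1" and "a minimum mean difference of 2.1 (in the breastfeeding knowledge score) and a SD of 3.4 for both groups", giving 43 per arm. The plan does not state sidedness; I take alpha = 0.05 two-sided, because a one-sided test would need only 33 per arm.

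**Reproducing the plan's figure.** The normal formula is n per arm = 2 × SD² × (1.96 + 0.8416)² / difference² = 2 × 3.4² × 2.8016² / 2.1² = 41.15, which rounds up to 42. With the t distribution, 42 per arm gives power of 79.9% and 43 per arm gives 80.8%. The plan's 43 is therefore reproduced.

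**Dilution.** Let f be the share of the app arm that cannot run the app. If those mothers gain nothing over leaflets, the expected difference is 2.1 × (1 − f). The standard error of the difference is 3.4 × √(2/43) = 0.733. The noncentrality is the diluted difference divided by 0.733, on 84 degrees of freedom, with critical value 1.989.

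| f (assumed) | Mothers among 43 | Difference | Noncentrality | Power |
|---|---|---|---|---|
| 0% | 0 | 2.10 | 2.864 | 80.8% |
| 1% | 0.4 | 2.08 | 2.835 | 80.0% |
| 2% | 0.9 | 2.06 | 2.807 | 79.2% |
| 5% | 2.2 | 1.99 | 2.721 | 76.7% |
| 10% | 4.3 | 1.89 | 2.578 | 72.2% |

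A normal approximation gives values about one point higher (81.7%, 80.9%, 80.1%, 77.7%, 73.2%), with the same pattern.

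**Simplifications.** The SD is held at 3.4. Mixing exposed and unexposed mothers would add f(1 − f) × 2.1² to the app-arm variance. At f = 10% that is 0.40 on 11.56, too little to change the picture. The calculation uses the plan's two-means comparison, not the double-difference regression, for which no variance inputs are given. It also uses the plan's net 43 per arm. Whether enrolling 112 mothers secures that number after losses is a separate question and is kept out of these figures.

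**The case against.** The strongest reply is that the criterion is functional. It asks for equipment needed to reach the tool, and if the tool runs only on Android and iOS, a computer-only mother arguably fails it whatever the bracket lists. The installation text also takes for granted that the mothers have mobile phones. This has some force, and a loose bracket may be all that is wrong. It does not remove the mismatch, because the bracket spells out what qualifies and names a computer. Nothing in the eligibility section requires a phone.

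The second reply is about size, and it stands. The documents give no share of computer-only mothers. The one related figure, in the State of the Art section, is that 82% of citizens reach the internet by mobile phone. It describes the general population and does not say how many own only a computer. At 1% to 2% the loss of power is under two points.

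Three stronger readings are tempting, and the documents support none of them:

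- A reader might infer that some randomised mothers will in fact be unable to receive the app. The text only fails to rule this out; it does not show that any such mother would be enrolled.
- A reader might infer that these mothers would be dropped after allocation, in the app arm only, which would break the randomised comparison. The plan provides for no such step, and its intention-to-treat commitment points the other way.
- A reader might infer that the criterion was written before a mobile app was chosen. Nothing dates the criterion.

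**Conclusion.** The mismatch is real and should be reconciled before mothers are randomised. As written, the device list permits a computer-only mother to be randomised to an app that is described only for Android and iOS and installed on phones. Under intention to treat, any such mother would move the estimate towards no difference.

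The effect on the trial cannot be quantified from the documents. Power starts at 80.8%, so about 1% of the app arm uses up the margin over 80%. At 5% the loss is about 4 points (80.8 − 76.7 = 4.1), and at 10% it is about 9 (80.8 − 72.2 = 8.6). These figures are illustrative. They rest on assumed values of f, no benefit over leaflets in unexposed mothers, an unchanged SD of 3.4, a two-sided 5% test and 43 completers per arm. The point merits correction because the edit is easy and works only before allocation, not because a large loss has been shown.

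**What to change.** - Remove computer from the trial's device criterion. Require an Android or iOS device able to run AmamantApp, and check this before randomisation for every mother, whichever arm she later enters. If a version usable on a computer exists, say so instead and keep the criterion.
- Make the installation text agree with the criterion on tablets: either include them in both places or drop them from both.
- Record device type at baseline for both arms and installation status in the app arm, so that the extent of non-receipt can be reported.
- State that a mother whose app cannot be installed after allocation stays in her arm for the intention-to-treat analysis.

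The cost is a short edit, a brief check at screening and two extra data items. If the criterion is narrowed, a few computer-only mothers become ineligible.
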